7. STUDY DRUG

7.1 Description of Investigational Agents

Ixazomib Capsules

The ixazomib drug product is provided in strengths of 4.0-, 3.0-, and 2.3-mg and 2.0-, 0.5-, and 0.2 mg capsules as the active boronic acid. The different dose strengths are differentiated by both capsule size and color as described below:

Dose Strength	Capsule Size	Capsule Color
4.0 mg	Size 4	Ivory
3.0 mg	Size 3	Light gray
2.3 mg	Size 2	Light pink
2.0 mg	Size 2	Swedish orange
0.5 mg	Size 3	Dark green
0.2 mg	Size 4	White opaque

For additional details, please see the ixazomib IB.

Lenalidomide

Lenalidomide, a thalidomide analogue, is an immunomodulatory agent with anti-angiogenic and anti-neoplastic properties. The chemical name is 3-(4-amino-1-oxo 1,3-dihydro-2H-isoindol-2-yl) piperidine-2,6-dione. The empirical formula for lenalidomide is C13H13N3O3, and the gram molecular weight is 259.3.

Lenalidomide is off-white to pale-yellow solid powder. It is soluble in organic solvent/ water mixtures, and buffered aqueous solvents. Lenalidomide is more soluble in organic solvents and low pH solutions. Solubility was significantly lower in less acidic buffers, ranging from about 0.4 to 0.5 mg/mL. Lenalidomide has an asymmetric carbon atom and can exist as the optically active forms S(-) and R(+), and is produced as a racemic mixture with a net optical rotation of zero. Lenalidomide is available in 5mg, 10mg, 15mg and 25mg capsules for PO administration. Each capsule contains lenalidomide as the active ingredient and the following inactive ingredients: lactose anhydrous, microcrystalline cellulose, croscarmellose sodium, and magnesium stearate. The 5 mg and 25 mg capsule shell contains gelatin, titanium dioxide and black ink. The 10 mg capsule shell contains gelatin, FD&C blue #2, yellow iron oxide, titanium dioxide and black ink. The 15 mg capsule shell contains gelatin, FD&C blue #2, titanium dioxide and black ink.

Dexamethasone

Dexamethasone is a commercially available PO drug, supplied as 2 and 4 mg tablets. It is a synthetic adrenocortical steroid and occurs as a white to off-white, odorless, crystalline powder. It is stable in air and practically insoluble in water.

7.2 Study Drug Administration

All protocol-specific criteria for administration of study drug must be met and documented before drug administration. Study drug will be administered or dispensed only to eligible patients under the supervision of the investigator or identified sub-investigator(s). Patients should be monitored for toxicity, as necessary, and doses of ixazomib should be modified as needed to accommodate patient tolerance to treatment; this may include symptomatic treatment, dose interruptions, and adjustments of ixazomib dose (see Section 7.3).

7.2.1 Experimental Arm

All Cycles are 28 days long.

Ixazomib Administration

Capsules of ixazomib will also be referred to as study drug. Study drug will be supplied by Millennium as capsules of 0.2-, 0.5-, and 2.0 mg, or as capsules of 2.3-, 3.0- and 4.0 mg ixazomib.

Subjects randomized to the experimental arm will receive Ixazomib as follows:

- Cycles 1-4: Ixazomib will be administered on Days 1, 8, and 15.
 - Cycle 1 will start at 3 mg. If 3 mg Ixazomib is well tolerated, the dose may be increased to 4 mg at the start of Cycle 2
- Cycles 5-12: Ixazomib will be administered on Days 1, 8, and 15 at the best tolerated dose established for the individual patient during Cycles 1-4.

Patients should be instructed to swallow ixazomib capsules whole, with water, and not to break, chew, or open the capsules. Ixazomib should be taken on an empty stomach (no food or drink) at least 1 hour before or 2 hours after a meal or any other medication. Each capsule should be swallowed separately with a sip of water. A total of approximately 8 ounces (240 mL) of water should be taken with the capsules.

Missed doses can be taken as soon as the patient remembers, if the next scheduled dose is 72 hours or more away. A double dose should not be taken to make up for a missed dose. If the patient vomits after taking a dose, the patient should not repeat the dose but should resume dosing at the time of the next scheduled dose.

Site staff will oversee the study subject taking day 1 doses of every cycle of all medications (IRd or R) during the visits to ensure proper administration. Site staff should not provide any study drug until dosing is to begin. Additionally, site staff will ensure that the study subject is adequately informed and understands dosing instructions for all medications. The site staff might consider asking the subject to repeat the dosing instructions to ensure his/her understanding, and allow the opportunity to ask questions. Dosing instructions should be repeated before a new dose of study drug is provided to the study subject.

Finally, dosing diaries will be completed by the site personnel including dates of doses to be taken, # of capsules to be taken/dosing day. In addition, where applicable, the site staff will cross out non-dosing days on the study subject's dosing diary at each dispensation visit.

Ixazomib Destruction

Investigational ixazomib (expired or end of study) should be destroyed on site according to the institution's standard operating procedure. Be sure to document removal and destruction on drug accountability logs.

Lenalidomide Administration

Lenalidomide will be provided in accordance with the lenalidomide REMS® program of Celgene Corporation. Per standard lenalidomide REMS® requirements, all physicians who prescribe lenalidomide for research subjects enrolled into this trial must be registered in and must comply with all requirements of the lenalidomide REMS® program. Prescriptions must be filled within 7 days. Only enough lenalidomide for one cycle of therapy will be supplied to the patient each cycle. Unused lenalidomide will be counted and documented by each site.

Subjects randomized to the experimental arm will receive lenalidomide as follows:

- Cycles 1-4: Lenalidomide will be administered on Days 1-21 at a dose of 25 mg.
- Cycles 5-12: Lenalidomide will be administered on Days 1-21 at the best tolerated dose.

Lenalidomide should be taken in the evening at approximately the same time each day. Lenalidomide is taken with water on a full or empty stomach. Subjects should not break, chew

or open capsules. Missed doses can be taken as soon as the patient remembers as long as it is less than 12 hours since the scheduled time. If it has been more than 12 hours, the dose should be skipped. Vomited doses will not be made up. Subjects should be instructed to never take lenalidomide past Day 21 of each cycle.

Dexamethasone Administration

Dexamethasone will ideally be best administered in the morning with a meal 2 hours before Ixazomib. If this is not possible, dexamethasone will be administered with a meal and at least 1 hour after ixazomib dose on days that they coincide (Days 1, 8, 15), as follows:

- Cycles 1-4: 40 mg PO per dose Days 1, 8, 15 and 22
 - Dexamethasone may administered as a split schedule of 20 mg PO or IV (pre-ixazomib during weeks 1-3 when ixazomib is administered) on Days 1, 2, 8, 9, 15, 16, 22, and 23 after discussion with the Lead Principal Investigator.
- Cycles 5-12: Dexamethasone discontinuation
 - Low dose of dexamethasone up to 20 mg per dose weekly on days 1, 8, 15, and 22 is allowed based on investigator determination of best tolerability of regimen.

Dexamethasone given on days without ixazomib and lenalidomide (Days 22) may be self-administered by the subject on an outpatient basis. Missed doses of dexamethasone will not be made up.

7.2.2 Control Arm

Lenalidomide Administration

Lenalidomide will be provided in accordance with the Lenalidomide REMS® program of Celgene Corporation. Per standard lenalidomide REMS® requirements, all physicians who prescribe lenalidomide for research subjects enrolled into this trial must be registered in and must comply with all requirements of the lenalidomide REMS® program. Prescriptions must be filled within 7 days. Only enough lenalidomide for one cycle of therapy will be supplied to the patient each cycle. Unused lenalidomide will be counted and documented by each site.

Subjects randomized to the control arm will receive lenalidomide as follows:

- Cycles 1-12: Lenalidomide will be continuously administered on Days 1-28 at a dose of either 10 mg or 15 mg.

- Lenalidomide administration may be given at 5 mg only if it is documented that this was the best last tolerated dose. 5 mg dosing requires Lead Principal Investigator approval.
- If the 10 mg dose is tolerated for 3 cycles – **off or on protocol** – the dose can be escalated to 15 mg.

Lenalidomide should be taken at approximately the same time each day. Lenalidomide is taken with water on a full or empty stomach. Subjects should not break, chew or open capsules. Late doses of lenalidomide should if possible be taken on the assigned day but should not be made up the next day. Vomited doses will not be made up.

7.3 Dose-Modification Guidelines

The following sections summarize dosing modifications for ixazomib, lenalidomide, and dexamethasone. Dose modifications different from those stated in the protocol must be discussed with the Lead Principal Investigator. Administration of ixazomib and/or lenalidomide will be discontinued in the event of any toxicity that, in the opinion of the Lead or Treating Investigator, warrants discontinuation.

In addition to dose reductions, administration of ixazomib and/or lenalidomide will be held temporarily in the event of a treatment-related toxicity, at the Treating Investigator's discretion. Study treatment may be re-introduced, if the event resolves back to the patient's baseline value or to \leq Grade 1 within 21 days; otherwise, study drug will be permanently discontinued. Any deviations from this plan must be approved by the Lead Principal Investigator.

Experimental Arm:

Table 7-1 Ixazomib Dose Adjustments

Nominal Ixazomib Dose	Dose -1	Dose -2	Dose -3
4 mg Days 1, 8, 15 (if escalated after Cycle 1)	3 mg	2.3 mg	Discontinue
3 mg Days 1,8,15	2.3mg	Discontinue	N/A

Table 7-2 Lenalidomide Dose Adjustments

Nominal Lenalidomide Dose	Dose -1	Dose -2	Dose -3	Dose -4	Dose -5
25 mg Days 1-21	20mg	15 mg	10 mg	5 mg	5 mg every other day

15 mg Days 1-21	10 mg	5 mg	5 mg every other day	Discontinue	N/A
1 mg Days 1-21	5 mg	5 mg every other day	Discontinue	N/A	N/A

Table 7-3 Dexamethasone Dose Adjustments*

Nominal Dexamethasone Dose	Dose -1	Dose -2	Dose -3	Dose -4
40 mg	20 mg	12 mg	8 mg	4 mg

*Split dosing of dexamethasone on days 1, 2, 8, 9, 15, 16, 22, and 23 may be implemented to control toxicities that do not require a dose reduction. Split dosing requires Lead Principal Investigator approval before implementing

Control Arm

Table 7-4 Lenalidomide Dose Adjustments

Nominal Lenalidomide Dose	Dose -1	Dose -2	Dose -3	Dose -4
15 mg Days 1-28	10 mg	5 mg	5 mg Days 1-21	5 mg every other day Days 1-21
10 mg Days 1-28	5 mg	5 mg Days 1-21	5 mg every other day Days 1-21	Discontinue

7.3.1 Recommended Criteria for Beginning or Delaying a Subsequent Treatment Cycle & Dose Modifications for Treatment Associated Toxicity

All treatment cycles are 28 days. For a new cycle of treatment to begin, the patient must meet the following criteria:

- ANC must be $\geq 1,000/\text{mm}^3$.
- Platelet count must be $\geq 75,000/\text{mm}^3$.
- All other non-hematologic toxicity (except for alopecia) must have resolved to \leq Grade 1 or to the patient's baseline condition

If the patient fails to meet the above-cited criteria for initiation of the next cycle of treatment, dosing should be delayed for 1 week. At the end of that time, the patient should be re-evaluated to determine whether the criteria have been met. If the patient continues to fail to meet the above-cited criteria, delay therapy and continue to reevaluate. The maximum delay before treatment should be discontinued will be 3 weeks or at the discretion of the Principal Investigator. Any delay greater than 21 days must be reviewed with the Lead Principal Investigator if the treating investigator believes that continued treatment is in the subject's best interest and confirmation of clinical benefit (absence of disease progression).

The following tables outline dosing recommendations for Ixazomib, lenalidomide and Dexamethasone.

Dosage adjustments for hematologic toxicity are outlined in Table 6-5

Table 7-5 Ixazomib and Lenalidomide Dose Adjustments for Hematologic Toxicities^{a, b}

Criteria	Action
If platelet count decreased to Grade 3 with clinically significant bleeding or Grade 4 $< 25 \times 10^9/L$ on any dosing day (other than Day 1)	
 • Ixazomib dose and lenalidomide should be withheld. • Complete blood count (CBC) with differential should be repeated at least twice weekly until the platelet counts have exceeded the pre-specified values (see Section 6.3.1) on at least 2 occasions. • Once resolved to Grade ≤ 1: 
 ○ 1st occurrence – decrease lenalidomide by 1 dose level; ixazomib may be reinitiated without dose reduction on the first occurrence. ○ 2nd occurrence - decrease ixazomib 1 dose level and resume len at its most recent dose ○ 3rd occurrence – decrease len 1 dose level from previous dose ○ 4th occurrence – decrease ixazomib 1 dose level from previous dose
Within-Cycle Dose Modifications	
Day 1 of Cycle Dose Modifications	
 • 1st occurrence – decrease lenalidomide 1 dose level • 2nd occurrence – decrease ixazomib 1 dose level • 3rd occurrence – decrease lenalidomide by 1 additional dose level • 4th occurrence – decrease ixazomib by 1 additional dose level
Neutrophil count (ANC) decreased Grade 3 (ANC 500-1000/mm ³) or > Grade 3 with fever (temperature $>38.5^{\circ}\text{C}$)	

Dosage adjustments for hematologic toxicity are outlined in Table 6-5

Table 7-5 Ixazomib and Lenalidomide Dose Adjustments for Hematologic Toxicities^{a, b}

Criteria	Action
Within-Cycle Dose Modifications	
 • Ixazomib dose and lenalidomide should be withheld. • Complete blood count (CBC) with differential should be repeated at least twice weekly until the ANC has exceeded the pre-specified values (see Section 6.3.1) on at least 2 occasions. • If neutropenia resolved to <Grade 2: 
 ◦ Lenalidomide decrease 1 dose level ◦ Ixazomib – resume at its most recent dose if ANC recovered prior to next planned dose and resume planned treatment cycle
Day 1 of Cycle Dose Modifications	
 • If neutropenia is the only toxicity for which a dose reduction is required, G-CSF may be used prophylactically, as per ASCO guidelines, for the subsequent cycle and dose maintained • For each subsequent occurrence of the same level of neutrophil count decrease, hold lenalidomide treatment and upon recovery of ANC to >1,000/mm³ resume as follows: 
 ◦ 1st occurrence – decrease lenalidomide 1 dose level ◦ 2nd occurrence – decrease ixazomib 1 dose level ◦ 3rd occurrence – decrease lenalidomide by 1 additional dose level; do not dose below 5mg daily
Grade 4 neutropenia (<500/mm³)	
Within Cycle Dose Modifications	
 • Ixazomib dose and lenalidomide should be withheld. • Complete blood count (CBC) with differential should be repeated at least twice weekly • If neutropenia resolved to <Grade 2 within the cycle: 
 ◦ Lenalidomide decrease 1 dose level below current dose level ◦ Ixazomib if prior to next planned dose, decrease 1 dose level

Dosage adjustments for hematologic toxicity are outlined in Table 6-5

Table 7-5 Ixazomib and Lenalidomide Dose Adjustments for Hematologic Toxicities^{a, b}

Criteria	Action
Day 1 of Cycle Dose Modifications	
 • Use of G-CSF as above • For each subsequent drop $<1,000/\text{mm}^3$ and recovery to $>1,000/\text{mm}^3$, decrease lenalidomide one dose level less than the previous dose, but do not dose below 5 mg daily

a) Both drugs may be reduced at the same time at the investigator's discretion
b) Doses held during a treatment cycle are not to be replaced

Treatment modifications due to ixazomib-related AEs are outlined in Table 6-6.

Table 7-6 Ixazomib Treatment Modification (Delays, Reductions, and Discontinuations) Due to Adverse Events (Non-Hematologic Toxicities)

Adverse Event (Severity)	Action on ixazomib	Further Considerations
Peripheral Neuropathy:		
Grade 1 peripheral neuropathy without pain	
 • No action 	Grade 1 signs and symptoms: asymptomatic; without pain or loss of function; clinical or diagnostic observations only [14]
New or worsening Grade 1 peripheral neuropathy with pain or Grade 2	
 • Hold ixazomib until resolution to Grade ≤ 1 without pain or baseline • Reduce ixazomib 1 dose level 	Grade 2 signs and symptoms: Moderate symptoms; limiting instrumental activities of daily living (ADL) [14]
New or worsening Grade 2 peripheral neuropathy with pain or Grade 3	
 • Hold ixazomib until resolution to Grade ≤ 1 without pain or baseline • Reduce ixazomib to next lower dose upon recovery 	Grade 3 signs and symptoms: severe symptoms; limiting self-care ADL; assistive device indicated [14]
New or worsening Grade 4 peripheral neuropathy	
 • Discontinue ixazomib 	

Table 7-6 Ixazomib Treatment Modification (Delays, Reductions, and Discontinuations) Due to Adverse Events (Non-Hematologic Toxicities)

Adverse Event (Severity)	Action on ixazomib	Further Considerations
Grade 2 Rash	
 Follow at least weekly Symptomatic recommendations as per section 6.6 	The investigator and project clinician may discuss considerations for dose modifications and symptom management.
Grade 3 non-hematologic toxicity judged to be related to ixazomib except for the following toxicity: 
 > Grade 3 nausea and/or emesis in the absence of optimal anti-emetic prophylaxis (section 6.7) > Grade 3 diarrhea that occurs in the absence of optimal supportive therapy (section 6.7) Grade 3 fatigue 	
 Hold ixazomib until resolution to Grade < 1 or baseline 
Subsequent recurrence Grade 3 that does not recover to < Grade 1 reduce ixazomib 1 dose level
	Symptomatic recommendations noted in Section 6.7 Monitor closely, take appropriate medical precautions, and provide appropriate symptomatic care
Grade 4 non-hematologic toxicities judged to be related to ixazomib	
 Consider permanently discontinuing ixazomib 	Exceptions are cases in which the investigator determines the patient is obtaining a clinical benefit
Delay of >2 weeks in the start of a subsequent cycle due to lack of toxicity recovery related to ixazomib	Hold ixazomib until resolution Reduce ixazomib 1 dose level	The maximum delay before treatment should be discontinued will be 3 weeks. If the maximum delay has been exceeded, resuming treatment can be considered after discussion with overall PI if clinical benefit is determined

Once ixazomib, lenalidomide, and/or dexamethasone are reduced for any toxicity, the dose may not be re-escalated.

Lenalidomide dose adjustments are allowed based on clinical and laboratory findings. Sequential lenalidomide dose reductions to 15 mg daily, 10 mg daily, and 5 mg daily are recommended for toxicity as indicated in Table 6-7.

Table 7-7 Lenalidomide Lenalidomide Dose Modifications Due to Non-Hematologic Toxicities

Adverse Event (Severity)	Action
Other Grade 3/4 toxicities	
 Hold lenalidomide treatment until toxicity has resolved to \leq Grade 1 or patient's baseline; restart at the next lower dose level (5mg less than the previous dose) 
 Do not dose below 5 mg daily
Rash	
 Non-blistering Rash, Grade 3 Non-blistering Rash, Grade 4 Desquamating (blistering rash) – Any grade 
 Hold lenalidomide and follow weekly. If the toxicity resolves to \leq Grade 1 prior to Day 21 of the current cycle, restart at 1 dose decrement and continue the cycle until Day 21 of the current cycle. Discontinue lenalidomide treatment Discontinue Lenalidomide treatment
Erythema multiforme \geq Grade 3	
 Discontinue lenalidomide treatment
Sinus Bradycardia / other new onset cardiac arrhythmia not present at baseline or deterioration of pre-existing cardiac arrhythmia	
 \leq Grade 2 \geq Grade 3 
 Hold lenalidomide, follow at least weekly. If the toxicity resolves to \leq Grade 1 prior to Day 21, restart at 1 dose decrement and continue the cycle until Day 21. Discontinue lenalidomide treatment
Allergic Reaction / Hypersensitivity	
 Grade 2-3 Grade 4 
 Hold Lenalidomide, follow at least weekly. If the toxicity resolves to \leq Grade 1 prior to Day 21, restart at 1 dose decrement and continue the cycle until Day 21. Discontinue lenalidomide treatment
Infection Grade 3-4	Hold lenalidomide, ixazomib, and dexamethasone until systemic treatment for infection is completed. If no neutropenia, restart all three drugs at same dose. If neutropenic, follow neutropenic instructions.
Herpes Zoster or simplex of any grade	Hold Lenalidomide, ixazomib, and dexamethasone until lesions are dry. Resume at same doses.
Renal Dysfunction	Dose reduce per lenalidomide package insert for impaired renal function; monitor renal function regularly
Venous Thrombosis/Embolism \geq Grade 3	Hold lenalidomide dose and adjust anticoagulation regimen; re-start at Treating Investigator's discretion at same dose
Hyperthyroidism or hypothyroidism	Omit lenalidomide for remainder of cycle, evaluate, and initiate appropriate therapy. Restart lenalidomide next cycle at 1 dose decrement
Congestive heart failure (CHF)	Any subject with NYHA stage III or IV CHF, whether or not lenalidomide related, must have the dose held until resolution or return to baseline. If CHF was felt to be lenalidomide related, reinstate by one dose decrement after return to baseline. If no resolution of CHF after 2 weeks, the subject will be withdrawn from the study.

Table 7-8 Treatment Guidelines for Toxicity Related to Dexamethasone

Body System	Symptom	Recommended Action
Gastrointestinal	Dyspepsia, gastric or duodenal ulcer, gastritis Grade 1-2 (requiring medical management)	Treat with H ₂ blockers, sucralfate, or omeprazole. If symptoms persist despite above measures, decrease dexamethasone dose by 1 dose level.
Gastrointestinal	≥ Grade 3 (requiring hospitalization or surgery)	Hold dexamethasone until symptoms adequately controlled. Restart at 1 dose decrement along with concurrent therapy with H ₂ blockers, sucralfate, or omeprazole. If symptoms persist despite above measures, discontinue dexamethasone permanently.
Gastrointestinal	Acute pancreatitis	Discontinue dexamethasone permanently.
Cardiovascular	Edema ≥ Grade 3 (limiting function and unresponsive to therapy or anasarca)	Diuretics as needed, and restart dexamethasone at 1 dose decrement; if edema persists despite above measures, decrease dose another level. Discontinue dexamethasone permanently if symptoms persist despite second reduction
Neurology	Confusion or mood alteration ≥ Grade 2 (interfering with function +/- interfering with activities of daily living)	Hold dexamethasone until symptoms resolve. Restart at 1 dose decrement. If symptoms persist despite above measures, discontinue dexamethasone permanently.
Musculoskeletal	Muscle weakness > Grade 2 (symptomatic and interfering with function +/- interfering with activities of daily living)	Decrease dexamethasone by 1 dose level. If weakness persists, decrease dose by 1 more dose level. Discontinue dexamethasone permanently if symptoms persist.
Metabolic	Hyperglycemia ≥ Grade 3	Treatment with insulin or PO hypoglycemic agents as needed. If uncontrolled despite above measures, decrease dose by 1 dose level until levels are satisfactory.

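### The toxicity rules in section 7.3.1 are written for IRd and have no control-arm version, so several steps give a control patient no dose change, stop dosing early, or conflict with Table 7-4

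*Combined protocol and SAP*

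**What the plan says.** Section 7.2.2 sets the control schedule: "Lenalidomide will be continuously administered on Days 1-28 at a dose of either 10 mg or 15 mg". Control patients receive no ixazomib and no protocol dexamethasone.

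Section 7.3 gives the control arm its own ladder under the title "Table 7-4 Lenalidomide Dose Adjustments". From 15 mg it runs 10 mg, 5 mg, 5 mg on Days 1-21, then 5 mg every other day on Days 1-21. From 10 mg it runs 5 mg, 5 mg on Days 1-21, 5 mg every other day on Days 1-21, then discontinuation. It lists levels and does not say what triggers a step.

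The triggers are in section 7.3.1, introduced by "The following tables outline dosing recommendations for Ixazomib, lenalidomide and Dexamethasone". No arm is named there. Table 7-5 (blood counts) alternates drugs in its platelet rows. The within-cycle instruction at the second event is "2nd occurrence - decrease ixazomib 1 dose level and resume len at its most recent dose". Table 7-7 (non-hematologic toxicity, lenalidomide) tells the site, after Grade 3 non-blistering rash, to "restart at 1 dose decrement and continue the cycle until Day 21 of the current cycle". The rows for arrhythmia of Grade 2 or less and for Grade 2-3 hypersensitivity also end dosing at Day 21. Tables 7-5 and 7-7 both contain an instruction to keep lenalidomide at or above 5 mg per day.

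**The concern.** Half of the randomized patients are governed by step-down rules that assume a drug they do not take and a 21-day schedule they are not on. Where the rule's only action is on ixazomib, a control patient who has already had one severe event returns to the same lenalidomide dose, or the site must devise its own response. In an open-label trial planned across 8 centers, the result may differ by site and by arm. This matters first for the safety of control patients with repeated events. It also matters for the secondary objective of comparing safety and tolerability between IRd and lenalidomide alone, because exposure after toxicity would partly reflect improvised rules.

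**Working it through.** No published figure is in dispute. The check applies Tables 7-5 and 7-7 literally to a control patient, using the Table 7-4 ladder and counting any step that acts only on ixazomib as no change. Occurrences are counted within each row, since the plan gives no rule for pooling them.

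**Table 7-5, control patient starting at 15 mg (lenalidomide dose after each step)**

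| Row | Drug acted on, by step | Lenalidomide after each step | Steps with no change |
|---|---|---|---|
| Platelets, within-cycle | len, ixa, len, ixa | 10, 10, 5, 5 mg | 2 of 4 |
| Platelets, Day 1 | len, ixa, len, ixa | 10, 10, 5, 5 mg | 2 of 4 |
| Grade 3 neutropenia, Day 1 (recurrences after a first event managed with G-CSF at the same dose) | len, ixa, len | 10, 10, 5 mg | 1 of 3 |
| Grade 3 neutropenia, within-cycle | len at each event | 10 mg, then 5 mg | none |
| Grade 4 neutropenia, within-cycle | len and ixa at each event | 10 mg, then 5 mg | none |
| Grade 4 neutropenia, Day 1 (drops after G-CSF use) | len at each subsequent drop | 10 mg, then 5 mg | none |

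The numbered steps total 4 + 4 + 3 = 11, and 2 + 2 + 1 = 5 of them leave a control patient unchanged. At the second within-cycle platelet step the text expressly resumes lenalidomide unchanged; at the other four it names only ixazomib and is silent on lenalidomide. Starting from 10 mg the platelet sequence is 5 mg, 5 mg, 5 mg Days 1-21, 5 mg Days 1-21, again with no change at steps 2 and 4.

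**Table 7-7, Day 21 rows.** Control dosing covers Days 1-28 and the three rows continue it to Day 21. Days dropped: 28 - 21 = 7, and 7/28 = 25% of the scheduled dosing days in that cycle. In IRd, dosing already ends at Day 21, so the loss is 0 of 21. The instruction never to take lenalidomide after Day 21 appears only in section 7.2.1, for the experimental arm. The 7 days are a maximum: a control patient already on a Days 1-21 level of Table 7-4 loses none.

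**Dose floor.** Over a 28-day cycle, 5 mg daily is 5 x 28 = 140 mg. Table 7-4 also lists 5 mg on Days 1-21 (5 x 21 = 105 mg) and 5 mg every other day on Days 1-21 (11 doses if begun on Day 1, 55 mg). The every-other-day level is below the floor on any reading. The Days 1-21 level keeps 5 mg on each dosing day but falls below 5 mg daily across the cycle. Table 7-2 gives the experimental arm an every-other-day level too, so the floor needs reconciling in both arms.

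**Other signs of IRd wording.** The Table 7-7 infection row speaks of restarting three drugs, and footnote a of Table 7-5 speaks of reducing both drugs together.

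**The case against.** The best defense is that the plan does not leave these patients unprotected. For within-cycle platelet events lenalidomide is withheld, counts are repeated at least twice weekly, and dosing resumes only after recovery to Grade 1 or better. The count thresholds for starting a cycle and the three-week limit on delay apply to both arms. The tables are called recommendations; the treating investigator may hold or discontinue for toxicity; and departures go to a single Lead Principal Investigator. All of that stands, and it lowers the severity. It does not supply a control-arm rule: footnote a presupposes two drugs, and a site that reduces lenalidomide at the second within-cycle platelet event is departing from the stated step.

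It may also be said that section 7.3 allows re-introduction whenever toxicity resolves within 21 days, so a later restart is not barred, and that some Table 7-4 levels already use Days 1-21. Both are correct. The mismatch remains for patients on a Days 1-28 level.

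A reader might infer that the ban "the dose may not be re-escalated" contradicts the control-arm provision that "the dose can be escalated to 15 mg". The documents do not support that: the first is a specific prohibition after a toxicity reduction, the second a general permission, and both can be followed if the first is read as the exception.

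**Conclusion.** The point holds as a drafting inconsistency that should be corrected. It covers the 2nd and 4th platelet steps, the 2nd listed recurrence of Day 1 Grade 3 neutropenia, the three Day 21 rows of Table 7-7, and the 5 mg floor against Table 7-4. It rests on a literal reading of tables that carry no arm restriction.

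Three stronger readings are tempting but unsupported:

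- That any second severe blood-count event leaves lenalidomide unchanged. Within-cycle Grade 3 neutropenia and both Grade 4 neutropenia rows do reduce it.
- That all 30 control patients are affected. All are subject to the tables, but the gap reaches only those with these events, and the documents give no control-arm event rate.
- That the primary endpoint is distorted because early stoppers are scored as failures (section 8.1.4). A same-dose restart or a Day 21 stop does not itself make a patient a failure, and the failure rule applies in both arms. Section 8.1 expects control conversion below 5%, that is fewer than 0.05 x 30 = 1.5 patients. No effect on this endpoint can be shown from the documents.

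**What to change.** Reconcile Tables 7-5 and 7-7 with Table 7-4 and section 7.2.2, so that every listed occurrence and every restart instruction has a stated action for the control arm, for example in a separate control-arm column. Settle in the same amendment how the 5 mg daily floor relates to the lower levels in Table 7-4, and in Table 7-2 for the experimental arm. The actions, levels and dosing days are clinical decisions for the sponsor; this review proposes none.

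The cost is a protocol amendment to the dose tables and notice to sites. It adds no patients, visits or procedures and does not touch the statistical design.
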